**Counting of symptoms during an ARI episode:**

Counting of the number of symptoms with new onset or worsening will be done per day and per assessment (clinical assessment or patient reported outcome in the eDiary or in the eDevice). Therefore, if a subject has several assessments at the same day (e.g. at ARI day 3-5, or by accident two RiiQs at the eDiary during the same day), the case definitions cannot be met by combining symptoms from different assessments, the required number of symptoms must be attained at one assessment.

For example, if at Day 3 a participant reports in the eDiary mild cough and the study staff reports mild wheezing at the same day, this participant does not meet case definition 2, because the 2 LRTI symptoms are reported by 2 different assessments. The participant would meet the case definition only if both symptoms were reported in the eDiary or if both were reported by the study staff in the clinical assessment.

Note: Patient reported outcomes reported in the eDiary and in the eDevice at the same day can be distinguished by the App type ID linked to the device and by the time of reporting.

#### **4.4.2.1.2. RSV RT-PCR Confirmation of the Considered ARI Episode**

Confirmation of RSV infection by RT-PCR (in midturbinate swabs or sputum sample, whenever available) will be performed at the central laboratory (GeneXpert assay only). For participants hospitalized with symptoms of an ARI, confirmation of RSV infection using an FDA-approved RT-PCR test at the local (hospital) laboratory will also be used for the analysis of case definitions if results from the central laboratory are not available. One positive sample (defined as any sample with a value above the limit of detection) is sufficient. RT-PCR results from samples that were out of stability are excluded from the analysis, regardless if they were RSV positive or RSV negative (except for the analysis based on the FAS).

Any midturbinate nasal swab and/or sputum sample taken within 7 days after onset of an ARI episode or during the ARI episode will be allocated to that ARI. In case of 2 consecutive ARI episodes, where the second ARI starts within 7 days after the onset of the first episode and the ARI Day 3-5 sample of the first episode is taken while the second episode is ongoing, then the midturbinate nasal swab and/or the sputum sample will be attributed to both ARIs.

#### **4.4.2.1.3. ARI Episode Duration**

The duration of an ARI episode is defined as: *Last day of symptoms above baseline - start date of ARI + 1*. The ARI Day 1 and ARI Day 3-5 visits are always taken into account for the duration if there is a new onset or worsening of a symptom. The ARI Day 29 is taken into account for the duration only if the RiiQ assessments reported by the participants on his/her home device go up to or exceed the ARI Day 29 visit date (actual date). In this case, ARI Day 29 site assessments occurring after this last RiiQ assessment reported by the participants on his/her home device (actual day) are not taken into account for the duration. End of Season as well as Day 365 and Day 730 visits are excluded when determining ARI end dates. Only URTI and LRTI symptoms from clinical assessment and patient reported outcome will be used in calculating the duration of an ARI episode (Table 8).

Moreover, for ARIs with no new onset or worsening of symptoms, duration will not be calculated.

For calculating the ARI duration, the following rules may be used:

- For all ARIs the start dates are reported in the CRF (=CE.CESTDTC where CETERM=ACUTE RESPIRATORY INFECTION and CE.CECAT= ‘’).

- Then a temporary end date for each ARI is created:
  - In case a participant has multiple ARIs, the temporary end date is set as a day before the start of the next ARI.
  - In case a participant has only one ARI, the temporary end date is set as the day of database cut off (15 May 2020).
- Search between the ARI start date and the temporary end date, for the last date the participant had a new onset or worsening of URTI or LRTI symptoms (Table 8), at the RiiQ assessments completed on his /her device and set it as ‘*enddate1*’.
- If the RiiQ assessments, between the ARI start date and the temporary end date, reported by the participants on his/her home device do not reach the actual ARI Day 29 visit date. Search between the ‘ARI Day 1’ and ‘ARI Day 3-5’ visits (both scheduled and unscheduled), for the last date the participant had a new onset or worsening of URTI or LRTI symptoms (Table 8), at the assessments collected during these visits and set it as ‘*enddate2*’.
- If the RiiQ assessments between the ARI start date and the temporary end date reported by the participants on his/her home device go up to or exceed the ARI Day 29 visit date (actual date). Search between the ‘ARI Day 1’, ‘ARI Day 3-5’ and ‘ARI Day 29’ visits (both scheduled and unscheduled), for the last date the participant had a new onset or worsening of URTI or LRTI symptoms (Table 8), at the assessments collected during these visits (clinical assessments and RiiQ) or at the participants device at home (RiiQ) during these dates and set it as ‘*enddate2*’.
- The ARI episode end date is defined as the maximum between ‘*enddate1*’ and ‘*enddate2*’.
- And the duration is defined as the *end date – ARI start date + 1*

**Note 1:** in case there is no new onset or worsening after the ARI start date then the ARI end date and the duration are considered missing.

**Note 2:** the start date of the ARI is always the date reported in the CE domain, even if the subject started reporting symptoms only later in the diary.

For example, see [Attachment 8](#)

#### 4.4.2.2. Analysis Methods

For each of the 3 primary endpoints the following will be performed: an exact Poisson regression will be fitted with the event rate, defined as the number of cases over the follow-up time (offset) as dependent variable and the vaccination group and age and being at increased risk for severe RSV disease (both as stratified) as independent variables. For cases, the follow-up time is defined as the time between vaccination and the occurrence of the first event (according to the considered endpoint), for non-cases, it is the time between vaccination and the end of season visit. In case the EOS visit is missing then the 15th of May 2020 will be used. However, for participants that discontinued before the end of the season and had an event (according to the considered endpoint), the follow-up time is defined as the time between vaccination and the occurrence of the first event and for participants that discontinued before having an event, follow-up time is the time between vaccination and the date of last contact (date of discontinuation).

Note: in case more than one end of season visits are available, the latest will be used to determine the follow up time.

Thus, all participants are included in the analysis according to their follow-up time. The exact one sided p-value corresponding to vaccination group will be compared with the one sided cut-off as described above (Section 4.4.1.1).

If the p-value is below the cut-off for at least 1 of the 3 primary endpoints, proof of concept is demonstrated. The individual exact 2-sided CIs ( $1-2 \times$  cut-off) for the VE (1-relative risk rate), measured by each of the 3 endpoints, will be calculated from the regression model described above and graphically depicted with forest plots.

The primary analysis will be performed on the PPE population, which will take cases into account with an onset at least 14 days after vaccination.

As sensitivity analyses the above Poisson model will be repeated similar to the primary analysis:

- based on the FAS (which also does not take into account the restriction on the onset [at least 14 days] and will count cases from vaccination on Day 1 onwards). RT-PCR results from samples that were out of stability, but tested RSV positive are taken into account in this analysis.
- based on the PPE set but taking into account only RT-PCR test results from the central laboratory (i.e., excluding the local test results for hospitalized participants)
- based on the PPE set but taking into account only RT-PCR test results from midturbinate swabs (excluding results from sputum samples)
- based on the PPE set but taking into account RT-PCR test results from both GeneXpert assay and GenMark assay, provided that GenMark is available for all ARIs. An ARI episode was considered as positive if GeneXpert is positive (regardless the GenMark result) or GeneXpert is negative but both GenMark and DDL indicate a positive result regardless the subtype.
- based on the PPE set but excluding coinfections with other respiratory viruses, based on GeneXpert and GenMark assay ([Attachment 3](#)). This should be detected in one of the scheduled nasal or sputum samples linked to the respective ARI but should not necessarily be detected in the same sample as the one that resulted in RSV confirmation.
- based on the PPE set but excluding coinfections with other respiratory viruses or bacteria based on GeneXpert, GenMark assay and the DDL bacterial assay ([Attachment 3](#)). This should be detected in one of the scheduled nasal or sputum samples linked to the respective ARI but should not necessarily be detected in the same sample as the one that resulted in RSV confirmation.
- based on the PPE set but only the participant reported symptoms (eDiary and eDevice) should be used to define case definitions.
- based on the PPE set but only the clinical assessment symptoms should be used to define case definitions
- based on the PPE set with age and increased risk status as collected (instead of as stratified) in case there are many discrepancies between as collected and as stratified.

- based on the PPE set but not taking into account cough for any of the case definitions
- based on the PPE set, but instead of focusing on the first occurrence of RT-PCR confirmed RSV-mediated LRTD, the number of events will be used as dependent variable and the offset will be defined as the time to discontinuation or end of season (whatever comes first). In case the end of season visit is missing, then the 15th of May 2020 will be used as end of season. And in cases, where more than one end of season visits are available, the latest will be used to determine the follow up time.

For these sensitivity analyses, corrected (based on each sensitivity) 2-sided confidence intervals for the VE will be calculated from these models and graphically depicted with forest plots.

Additional sensitivity analyses will include an exact binomial test ([Attachment 6](#)), not taking into account the strata, based on the PPE population and the FAS. The VE (=1- relative risk) and the corresponding corrected 2-sided CI based on the exact binomial will be calculated as well.

Moreover, similar Poisson models will be executed for the subgroups defined in Section 2.4. The 95% 2-sided CI for the VE (1-relative risk rate) will be calculated from these regression models (subgroup analyses) and graphically depicted with forest plots.

In case the Poisson model for one of the above analyses does not converge, the model for the considered analysis will be fitted with only the vaccination group as independent variable.

The number of participants (and percentages) fulfilling the case definitions for each analysis (primary, sensitivity and subgroup) in both groups will be calculated and graphically depicted with bar plots.

For subjects with RT-PCR-confirmed RSV-mediated LRTD based on the 3 case definitions, the median duration of the ARI episode and the median number of days meeting each case definition will be summarized. Moreover, time to first occurrence since vaccination of each case definition per group will be graphically presented with reverse Kaplan-Meier curves.

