#### **New onset or worsening of symptoms:**

To determine new onset or worsening of symptoms, symptoms should be compared with the respective baseline of the season wherein the episode started:

- Clinical assessment by the site staff will be compared with clinical assessment baseline by the site staff.
- Patient reported outcomes reported on the site's eDevice and on the participants eDiary will be compared with the baseline patient reported outcomes.

Symptoms present during an ARI episode but not at the baseline assessment will be considered as symptoms with a new onset. Symptoms present at the baseline assessment that become worse (higher severity) during the ARI episode will be considered as worsening symptoms.

For assessments that are numerically scored (Decreased oxygen, tachypnea, and fever) new onset or worsening is defined as follows:

- Decreased oxygen saturation is defined as:
  - oxygen saturation of  $<90\%$  for participants with a baseline oxygen saturation of  $\geq 90\%$  or a missing baseline at randomization (new onset)
  - for participants with baseline oxygen saturation  $<90\%$ , decreased oxygen saturation is defined as a  $\geq 3\%$  decrease in their oxygen saturation from baseline (worsening).
- Tachypnea is defined by respiratory rate (RR)  $>20$  breaths per minute:
  - For subjects with baseline RR  $\leq 20$  or a missing baseline, a value  $>20$  is considered a new onset.
  - For subjects with baseline RR  $>20$  (and  $\leq 25$ ), a value  $>25$  is considered a worsening.
- Fever: all temperatures  $>37.8^{\circ}\text{C}$  during an ARI episode will be considered as a fever, regardless of the baseline temperature of the participant. For example, if a subject has baseline temperature of 37.9 degrees Celsius and during the ARI episode his temperature of is again 37.9 degrees Celsius, it will be counted as a systemic symptom of fever.

Note 1: Shortness of breath and respiratory effort reported at the clinical assessment form will not be taken into account for the case definitions.

Note 2: If a participant at the clinical assessment reported a new onset or worsening of dyspnea and had decreased oxygen saturation, then it counts only as one symptom towards the case definitions. Similarly, if a participant had a new onset or worsening of wheezing and rhonchi, rales or other sign of consolidation, it also counts as one symptom.

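### In the all-events sensitivity analysis, one RSV-positive sample can confirm two consecutive ARIs and so be counted as two events

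*SAP*

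**What the plan says.** Four rules in the SAP meet here.

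- **Confirmation (Section 4.4.2.1.2).** A single positive is enough: "One positive sample (defined as any sample with a value above the limit of detection) is sufficient". For two consecutive episodes, "where the second ARI starts within 7 days after the onset of the first episode", and where the first episode's Day 3-5 sample is collected during the second, "then the midturbinate nasal swab and/or the sputum sample will be attributed to both ARIs".
- **Symptoms (Section 4.4.2.1.1).** New onset or worsening has a fixed reference: "symptoms should be compared with the respective baseline of the season wherein the episode started". Within an episode, "the required number of symptoms must be attained at one assessment".
- **Episode boundaries (Section 4.4.2.1.3).** For the duration calculation, "In case a participant has multiple ARIs, the temporary end date is set as a day before the start of the next ARI".
- **All-events analysis (Section 4.4.2.2).** The last of the eleven bulleted Poisson sensitivity analyses keeps the PPE set and the Poisson model but replaces first occurrence: "the number of events will be used as dependent variable". Follow-up then runs on after an event, until the participant leaves the study or the season closes.

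The rules that select one ARI per participant (Sections 4.5.1.1, 4.8.1 and 4.11.1, and the sections that refer to them) cover patient-reported outcomes, clinical assessment, medical resource use and related analyses. None is applied to the all-events count.

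**The concern.** The shared-sample rule is harmless where each participant contributes at most one event, and it was evidently written with those endpoints in mind. It is not carried through to the one primary-endpoint analysis that counts every event. There, two ARIs confirmed by the same swab enter as two events, although the evidence is of one infection.

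The symptom reference makes this possible. Because symptoms are compared with the season baseline and not with the state between episodes, symptoms that persist through one illness can qualify in both ARIs.

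At stake is the credibility of a supportive analysis that is shown with a corrected confidence interval beside the primary result. Its estimate can shift by an artefact, and the unmodified Poisson model treats the duplicate as new information.

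**Working it through.** **Conditions for a double count.** All must hold:
1. The second ARI starts within 7 days of the first onset.
2. The first episode's Day 3-5 sample is taken while the second is ongoing.
3. That sample is RSV-positive.
4. Each ARI separately reaches the required symptom count at one assessment.

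Nothing in the SAP then reduces the two events to one.

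**The SAP's own figure.** It gives none for the all-events analysis. The cut-off that applies to sensitivity analyses is illustrated in Section 4.4.1.1 as 0.0335, then 0.0175 per case definition. A one-sided Pocock boundary with correlations sqrt(IF_i/IF_j) gives 0.03355 at (0.7, 1), then 0.01746 at (0.56, 0.72, 1). The example reproduces, and 0.0175 is used below as a fixed illustrative cut-off. In practice the level would be recalculated for each sensitivity analysis.

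**Effect on VE.** Assumed counts of 5 vaccine and 16 placebo events, 1:1 allocation, equal follow-up, no strata. The offset does not stop at the event, so a duplicate adds to the count only.
- No duplicate: 1 − 5/16 = 68.8%
- One placebo duplicate: 1 − 5/17 = 70.6%
- One vaccine duplicate: 1 − 6/16 = 62.5%
- Every infection duplicated in both arms: 1 − 10/32 = 68.8%

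**Effect on the p-value.** Total of 18 Case Definition #2 events as in the Section 4.4.1.1 example, with an assumed split of 4 vaccine and 14 placebo; exact conditional binomial test with probability 0.5, one-sided.
- No duplicate: p = 0.0154, VE = 1 − 4/14 = 71.4%
- One placebo duplicate: p = 0.0096, VE = 1 − 4/15 = 73.3%
- One vaccine duplicate: p = 0.0318, VE = 1 − 5/14 = 64.3%, now above 0.0175

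**Effect on the variance.** Let each infection be counted m times, with m = 2 with probability d and m = 1 otherwise, equally in both arms. Then E[m] = 1 + d and E[m²] = (1 − d) + 4d = 1 + 3d. For a Poisson number of infections, the true variance of the count divided by the Poisson variance is E[m²]/E[m] = (1 + 3d)/(1 + d).
- d = 5%: 1.15/1.05 = 1.10
- d = 10%: 1.30/1.10 = 1.18
- d = 20%: 1.60/1.20 = 1.33

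**Actual one-sided error at nominal 0.0175** (same exact test, no strata or offset):

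| Infections | d = 0 | 5% | 10% | 20% | 50% |
|---|---|---|---|---|---|
| 18 | 0.0154 | 0.0142 | 0.0160 | 0.0238 | 0.0369 |
| 50 | 0.0164 | 0.0152 | 0.0196 | 0.0261 | 0.0432 |

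The share d is not given in the SAP; the range is an assumption.

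**The case against.** The strongest reply is that this is a remote case in one of eleven bulleted sensitivity analyses. Several strands of it stand.

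- **No decision depends on it.** A reader might infer that the primary result or the proof-of-concept decision is exposed. It is not: both use first occurrence, at most one event per participant. Nor does the all-events count appear among the sensitivity analyses for later seasons in Section 5.4.1.2.
- **No direction of bias is shown.** It is tempting to conclude that efficacy would be overstated. Nothing in the SAP suggests that duplication differs by arm; a vaccine duplicate lowers VE, and equal duplication leaves its expectation about unchanged.
- **The error inflation is small if duplicates are rare.** A reader might infer that the interval is materially invalid. At shares of 5% to 10% the conservatism of the exact test largely absorbs the effect: with 18 infections the error stays below 0.0175, and with 50 it reaches 0.0196 at 10%. Clear inflation needs shares of 20% or more, for which the SAP gives no support.
- **The protocol may restrict when a new ARI can be opened.** The boundary rule in Section 4.4.2.1.3 concerns duration and does not by itself prove that no symptom-free gap is required. Since Section 4.4.2.1.2 provides explicitly for ARIs this close together, this can limit the frequency but does not remove the mechanism.
- **A reader could notice.** Section 4.4.2.2 also tabulates participants meeting each case definition for every analysis. That shows that participants and events differ in number, but not which extra events share a sample.

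Correlation between genuine repeat infections in one participant is a separate matter, and removing shared-sample duplicates does not address it.

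**Conclusion.** The gap is real and minor. Followed as written, the SAP can count one swab-proven infection as two events in the all-events Poisson sensitivity analysis, provided that both ARIs separately meet the case definition. The first-occurrence analyses are untouched.

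The frequency is unknown and probably low. With counts as small as those in the SAP's example, a single duplicate moves VE by about 2 points upward (placebo) or about 6 to 7 points downward (vaccine), and can carry a borderline p-value across the cut-off. With equal duplication, the harm is an understated variance, by a factor of about 1.10 to 1.18 at shares of 5% to 10%.

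These sizes rest on assumed splits (5/16 and 4/14), equal follow-up, no strata and an assumed duplicate share. That the model treats the two events as independent follows from using an unmodified Poisson count; the SAP does not say so in words.

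**What to change.** Add a sentence to the all-events bullet in Section 4.4.2.2: ARIs whose RSV confirmation rests on the same positive sample count as one event, dated at the earliest onset and classified by the strictest case definition met; a second event is counted only if that ARI has a positive sample of its own.

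The criterion should be the shared sample, not closeness of onset. Merging all ARIs that start within 7 days of each other would also combine episodes that each have their own positive result.

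The cost is one sentence and a de-duplication step on data already collected. The primary analysis does not change. Section 1.6 of this amendment refers to the season 1 primary analysis in the past tense. If that sensitivity analysis has already been run, present the corrected count as a labelled re-run beside the existing one, with the number of events merged in each arm.

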#### **4.4.3. Major Secondary Endpoints**

##### **4.4.3.1. Definition**

First occurrence of a considered endpoint is defined as the first day of symptoms of the first ARI episode where the criteria for the respective endpoint are fulfilled on at least one assessment of the considered episode. The secondary objectives are defined as follows:

- **First occurrence of any RT-PCR-confirmed RSV ARI**

This is defined as any acute respiratory infection (ARI) in combination with RSV confirmation by RT-PCR in at least one of the samples taken up to 7 days after the onset of the ARI episode or during the ARI episode, see Section 4.4.2.1.2.

**Any ARI** is defined as new onset or worsening of any of the LRTI and URTI clinical symptoms. Systemic symptoms will not be taken into account. New onset or worsening of symptoms is

determined in a similar way as for the primary endpoint (Section 4.4.2.1.1). Table 8 contains the LRTI and URTI symptoms collected in the RiiQ and the clinical assessment.

ARIs indicated by the site as being initiated in error by the participant, with no RT-PCR swab linked to them will not be taken into account in the analysis.

**Table 8: Symptoms of LRTI and URTI as per RiiQ or Clinical Assessment**

	RiiQ Term	Clinical Assessment Term (ARI Days 3-5 Clinical Visit)
Symptoms of LRTI	Cough	Cough
	Short of breath	Dyspnea or decreased oxygen saturation* or Shortness of breath
	Coughing up phlegm (sputum)	Sputum production
	Wheezing	Wheezing; rhonchi, rales or other sign of consolidation
		Tachypnea
		Respiratory Effort
Symptoms of URTI	Sore Throat	Nasal discharge
	Nasal congestion	Pharyngitis
		Sinus tenderness

Any midturbinate nasal swab and/or sputum sample taken within 7 days after onset of an ARI episode or during the ARI episode will be allocated to that ARI. In case of 2 consecutive ARI episodes, where the second ARI starts within 7 days after the onset of the first episode and the ARI Day 3-5 sample of the first episode is taken while the second episode is ongoing, then the midturbinate nasal swab and/or the sputum sample will be attributed to both ARIs.

For calculating the duration of an ARI episode, the first day of symptoms above baseline and the last day of symptoms above baseline will be considered. Days with missing symptom assessments during an ARI episode will be considered part of the ARI episode. For more details, refer to Section 4.4.2.1.3.

Note: Shortness of breath and respiratory effort reported at the clinical assessment form will be taken into account for the definition of any ARI disease.

Note: RSV RT-PCR confirmation is defined based on the GeneXpert assay only.

